**Procedure success**

Lesion success (see definition above) without the occurrence of major adverse cardiac events (see definition above) during the index procedure hospital stay (maximum of 7 days). In the setting of multiple target lesions, all lesions must meet the lesion success criteria to have a patient-level procedure success.

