#### 2.2.2.2 Device Success

Device success is defined as attainment of <30% in-stent residual stenosis of the target lesion measured by QCA using the assigned device [evaluated post-procedure]. Lesions treated with multiple stents in which one stent is an assigned device and  $\geq 1$  is not the assigned device are considered as device failures.

This analysis is a lesion-level analysis performed in the ITT subject population. The primary analysis will include all target lesions in which implantation of the assigned device is attempted in the denominator. As a secondary analysis, the device success analysis will include all target lesions in the denominator, whether or not an attempt to implant the assigned device was made.

In addition, lesions without device success will be reported according to the following classification adapted from the 2019 EAPCI/ESC position statement (Chang et al. Defining Device Success for Percutaneous Coronary Intervention Trials: A Position Statement from the European Association of Percutaneous Cardiovascular Interventions of the European Society of Cardiology. *Eurointervention* 2019; Jaa-642 2019, doi 10.4244/EIJ-D-19-00552) [1] in a lesion-level analysis:

	FORM	Document No BIO-TMP-0702 Revision: 00
	TITLE Statistical Analysis Plan	Effective date: 16-Mar-2018 Department: BIO

- 1) PCI was not attempted
- 2) No device implanted (with or without implant attempt)
- 3) Non-assigned device implanted without attempt to use the assigned device
- 4) Unsuccessful device delivery (i.e., implant attempted but no device ultimately implanted)
  - a) Without crossover to non-assigned devices (i.e., attempted implant of assigned device; did not attempt to implant unassigned device)
  - b) Crossover to non-assigned devices, but still unsuccessful (i.e., attempted to implant assigned device; attempted implant of unassigned device)
- 5) Device implanted outside the intended location
- 6) Non-assigned device implanted after a failed attempt to use the assigned device
- 7) Non-assigned device implanted after successful implantation of assigned device(s)
- 8) Residual stenosis above accepted thresholds (NOTE: threshold is  $\geq 30\%$  based on protocol definition of device success)

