#### **2.2.2.3 Procedure Success**

Procedure success is defined as lesion success without the occurrence of in-hospital major adverse cardiac events (MACE) [evaluated in-hospital]. MACE is a composite of all-cause death, myocardial infarction, and target vessel revascularization and will be adjudicated by an independent Clinical Events Committee (CEC). The myocardial infarction (MI) events will be adjudicated per the modified Third Universal Definition.

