#### **2.2.3.4 Stent Thrombosis (Definite or Probable)**

Stent thrombosis is defined as definite, probable, or possible according to the following ARC definitions, and classified as early, late, or very late according to the timing criteria below:

- **Definite stent thrombosis:** Confirmed by angiographic or pathological evidence:
  - Angiographic confirmation of stent thrombosis: The presence of an intracoronary thrombus that originates in the stent or in the segment 5 mm proximal or distal to the stent and presence of at least 1 of the following criteria within a 48-hour time window:
    - Acute onset of ischemic symptoms at rest
    - New ischemic ECG changes that suggest acute ischemia
    - Typical rise and fall in cardiac biomarkers (refer to definition of spontaneous MI)
    - Nonocclusive thrombus. Intracoronary thrombus is defined as a (spheric, ovoid, or irregular) noncalcified filling defect or lucency surrounded by contrast material (on 3 sides or within a coronary stenosis) seen in multiple projects, or persistence of contrast material within the lumen, or a visible embolization of intraluminal material downstream.
    - Occlusive thrombus: TIMI 0 or 1 in stent or proximal to a stent up to the most adjacent proximal side branch or main branch (if originating from the side branch)

NOTE: The incidental angiographic documentation of stent occlusion in the absence of clinical signs or symptoms is not considered a confirmed stent thrombosis (silent occlusion).

- Pathologic confirmation of stent thrombosis: Evidence of recent thrombus within the stent determined at autopsy or via examination of tissue retrieved following thrombectomy.
- **Probable stent thrombosis:** Clinical definition of probably stent thrombosis is considered to have occurred after intracoronary stenting in the following cases:

	FORM	Document No: BIO-TMP-0702 Revision: 00
	TITLE Statistical Analysis Plan	Effective date: 16-Mar-2018 Department: BIO

- Any unexplained death within the first 30 days
- Irrespective of the time after the index procedure, any MI that is related to documented acute ischemia in the territory of the implanted stent without angiographic confirmation of stent thrombosis and in the absence of any other obvious cause

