All time-to-event analyses will be performed with time defined from date of randomization to first occurrence of an event. Subjects without events will be censored at their early withdrawal date or the last known event-free time point. If this event-free time point occurs after the analysis time point, the days to event variable will be set equal to the analysis time point so that the patient will be included in the analysis (e.g. if the last data point was collected at 1 year and 2 weeks post-procedure, for the 1-year analysis, this subject will be censored at exactly 1 year (365 days)). When analyzing composite endpoints, time is measured from randomization to the first event (days).

	FORM	Document No BIO-TMP-0702 Revision: 00
	TITLE Statistical Analysis Plan	Effective date: 16-Mar-2018 Department: BIO

Per protocol, patients may have multiple target lesions treated. For patient level endpoints, only one lesion per subject is required to meet the criteria for the endpoint. All clinical, procedural, and safety endpoints are summarized on a patient level, except when noted. All Angiographic Core Lab variables will be summarized on a lesion level.

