### 5.3.2 Secondary Efficacy Endpoints

Lesion Success will be assessed on a lesion level, performed on the ITT analysis population, and presented for overall subjects and by treatment arm. The analysis of Device Success will include all

	FORM	Document No BIO-TMP-0702 Revision: 00
	TITLE Statistical Analysis Plan	Effective date: 16-Mar-2018 Department: BIO

target lesions in which the assigned device is attempted in the denominator [1]. As a secondary analysis, the device success analysis will include all target lesions in the denominator, whether or not an attempt to implant the assigned device was made.

No formal hypothesis testing will be performed. Both endpoints will be compared descriptively between the treatment arms using a generalized linear mixed model that accounts for the clustering effect of multiple lesions per subject. The model includes treatment as a fixed effect and subject as a random effect. Two sided 95% CI for the estimated difference and p-values will be reported.

Procedural success and in- hospital TVR, TLR, TVF, and TLF events will be evaluated in the ITT analysis population. No formal hypothesis testing will be performed. Descriptive statistics will include count, percentage, and sample size. Subjects with missing data will be excluded from the denominator. Differences between the two treatment arms will be summarized descriptively with the difference in percentages, the asymptotic 95% confidence interval for the difference of two percentages, and a p-value based on a chi-squared test. If 20% or more of the expected cell frequencies are less than 5 then a Fisher's Exact Test will be used to test for differences in proportions.

Survival analysis techniques, as detailed in Section 4.3, will be used to analyze the TVR, TLR, TVF, and TLF events at 30 days, 6 months, and 1, 2, 3, 4, and 5 years. Summary statistics will include Kaplan-Meier estimated event rates and number of events. The log-rank test will be used for comparing treatments. Hazard ratios and the associated two-sided confidence intervals (Wald's CI) will be estimated by Cox proportional hazards model, including treatment as a covariate.

A secondary analysis of all secondary efficacy endpoints will also be performed in the PP analysis population.

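### Read literally, the one-lesion rule in SAP 4.3 reverses the protocol's all-lesions condition for procedure success; separately, the residual-stenosis formula in SAP 2.2.2.1 does not match SAP Table 2

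*SAP*

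**What the plan says.** SAP 4.3 notes that a subject may have several target lesions treated and then gives a counting rule: "For patient level endpoints, only one lesion per subject is required to meet the criteria for the endpoint". The next sentence sets the level of analysis: "All clinical, procedural, and safety endpoints are summarized on a patient level, except when noted".

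Two of the three acute success endpoints are noted as exceptions. On device success, SAP 2.2.2.2 says: "This analysis is a lesion-level analysis performed in the ITT subject population". SAP 5.3.2 places lesion success at lesion level as well. Procedure success is not noted. SAP 5.3.2 says: "Procedural success and in- hospital TVR, TLR, TVF, and TLF events will be evaluated in the ITT analysis population". It then prescribes counts and percentages with subjects as the denominator. The definition in SAP 2.2.2.3 begins "Procedure success is defined as lesion success without the occurrence of in-hospital major adverse cardiac events (MACE" and does not say how several lesions in one subject are combined.

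The Procedure success entry in protocol Appendix A (17.1) does say: "all lesions must meet the lesion success criteria to have a patient-level procedure success". It also limits the period in which MACE counts: "during the index procedure hospital stay (maximum of 7 days". The protocol synopsis and protocol 5.3.3.2.3 use the same short definition as SAP 2.2.2.3. The all-lesions condition and the 7-day maximum appear only in Appendix A.

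On the underlying measurement, SAP 2.2.2.1 prints in-stent residual stenosis with the bracket closed before the division. SAP Table 2 gives in-stent percent diameter stenosis from the same core-laboratory quantities, with the division inside the bracket.

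**The concern.** A rule that one lesion is enough is right for a failure endpoint. Protocol 11.4.3 and SAP 5.2.1 count a subject as a TLF failure if any target lesion has a clinically-driven revascularization. Applied to a success endpoint, the same words turn an all-lesions condition into an any-lesion condition. A subject with two target lesions, one of which failed, would then meet the lesion-success part of procedure success. Protocol 6.2.1.2.1 allows up to three target lesions, so such subjects are expected.

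The missing 7-day limit has a smaller effect. A first MACE after day 7 of a longer index stay would count against procedure success under the short definition but not under Appendix A.

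The printed formula, if it is what the SAP really contains, would pass lesions that fail under Table 2. It feeds lesion success, device success (which uses the same threshold) and, through lesion success, procedure success.

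**Working it through.** **Counting rule: texts side by side**

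1. SAP 4.3: one lesion is enough for a patient-level endpoint, and procedural endpoints are patient-level unless noted.
2. SAP 2.2.2.2 and 5.3.2: device and lesion success are noted as lesion-level, so the rule does not reach them directly.
3. SAP 2.2.2.3 and 5.3.2: procedure success is analysed per subject, with no exemption and no rule for combining lesions.
4. Protocol Appendix A: every target lesion must succeed.

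Items 1 and 3 together give the opposite of item 4.

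**Counting rule: size**

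Neither document states a procedure-success figure to reproduce. Nor do they give a per-lesion success rate p, a within-subject correlation r or a share of multi-lesion subjects, so all three are assumptions. For two lesions, considering the lesion-success part only:

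- P(all succeed) = p² + r·p(1 − p)
- P(at least one succeeds) = 2p − P(all succeed)
- Gap = 2p(1 − p)(1 − r)

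| p | r | All lesions (Appendix A) | At least one (SAP 4.3, literal) | Gap, points |
|---|---|---|---|---|
| 0.90 | 0 | 81.0% | 99.0% | 18.0 |
| 0.99 | 0 | 98.01% | 99.99% | 1.98 |
| 0.90 | 0.5 | 85.5% | 94.5% | 9.0 |
| 0.99 | 0.5 | 98.505% | 99.495% | 0.99 |
| any | 1 | p | p | 0 |

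These gaps apply only to two-lesion subjects. Across an arm the gap is multiplied by their share m. With an assumed m of 10% to 30% and independent lesions, m × 2p(1 − p) is 1.8 to 5.4 points at p = 0.90 and 0.2 to 0.6 points at p = 0.99. A correlation of 0.5 halves these.

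**Formula**

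The threshold for lesion success is a residual stenosis under 30% (SAP 2.2.2.1).

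- As printed in SAP 2.2.2.1: A = 100 × (1 − MLD)/RVD
- SAP Table 2: B = 100 × (1 − MLD/RVD)

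| MLD, mm | RVD, mm | A | B |
|---|---|---|---|
| 1.5 | 3.0 | 100 × (−0.5)/3.0 = −16.7% (pass) | 100 × (1 − 0.5) = 50.0% (fail) |
| 2.0 | 3.0 | −33.3% (pass) | 33.3% (fail) |
| 2.5 | 3.0 | −50.0% (pass) | 16.7% (pass) |

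A is negative whenever MLD exceeds 1 mm. Solving each for under 30% gives MLD > 1 − 0.3 × RVD for A and MLD > 0.7 × RVD for B. At RVD 3.0 mm these are 0.10 mm and 2.10 mm. At RVD 2.25 mm they are 0.325 mm and 1.575 mm. At RVD 4.0 mm, A is always met and B needs more than 2.80 mm. Taken literally, A would pass almost every lesion.

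**The case against.** The strongest reply is that SAP 4.3 was never meant for success endpoints. The sentence follows paragraphs on events, censoring and time to first event, and SAP 5.2.1 states the same any-lesion idea for TLF. Appendix A gives a specific rule, and SAP 1.0 says that the SAP supplements the protocol and that significant modifications to protocol-specified analyses will be reflected in an amendment or the study report. This is probably the intended reading. It does not remove the gap: SAP 4.3 is not limited to failures, it names procedural endpoints, and the all-lesions condition sits only in a protocol appendix. The independent programmer in SAP 4.0 validates analyses as the SAP defines them, so validation from the SAP alone could reproduce the one-lesion rule.

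A second reply is that SAP 2.2.2.3 repeats the protocol's own endpoint wording. That stands. The missing all-lesions and 7-day details are inherited from the short definition in the protocol.

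A third reply concerns the formula. The equation was extracted from a PDF by a program, Table 2 has the sensible form, and SAP 2.3 derives the QCA variables from it. Negative stenoses would be obvious in any output. This stands as a reason to check the PDF first and to expect the error, if real, to be caught.

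A fourth reply is that failed lesions stay visible, because lesion success is reported at lesion level and Listing 7 in SAP 7.1 covers lesion and procedure success. That also stands and limits the harm.

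**Conclusion.** The point holds as a low-severity inconsistency. Followed as written, SAP 4.3 gives procedure success an any-lesion meaning where Appendix A requires all lesions. The formula in SAP 2.2.2.1, if the PDF confirms it, disagrees with Table 2. For a two-lesion subject the first would raise the lesion-success part by 18.0 to 2.0 points (independent lesions) or 9.0 to 1.0 points (correlation 0.5), for an assumed per-lesion success of 0.90 to 0.99. The whole-arm effect is smaller and cannot be fixed from the documents.

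The documents do not support several stronger inferences:

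- **That the SAP deliberately redefined procedure success.** Its short definition matches the protocol synopsis and 5.3.3.2.3, and the protocol's version history names no such change.
- **That SAP 4.3 is the SAP's only rule for subjects with several lesions.** SAP 5.2.1 states one for TLF, and SAP 5.3.2 models clustering for lesion and device success.
- **That the bracket is an established error.** It has to be confirmed in the source PDF.
- **That the comparison between arms is biased, or that trial conclusions are at risk.** The same rules apply to both arms. Procedure, lesion and device success have no formal hypothesis test (SAP 5.3.2). The 12-month TLF non-inferiority test and the landmark TLF analysis use none of this.

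It is still worth correcting, because SAP 5.3.2 reports procedure success with a between-arm difference, a 95% confidence interval and a p-value.

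**What to change.** - **SAP 4.3:** limit the one-lesion rule to failure (event) endpoints. The limited rule should still cover stent thrombosis: SAP 2.2.3.4 says "Stent thrombosis is defined as definite, probable, or possible according to the following ARC definitions" but gives no rule of its own for subjects with several lesions.
- **SAP 2.2.2.3:** refer to the Appendix A definition, so that every target lesion must meet lesion success. This also brings in the 7-day limit.
- **SAP 2.2.2.1:** check the source PDF. If it shows the bracket as extracted, write 100 × (1 − mean(MIN1, MIN2)/mean(IS1, IS2)) or refer to Table 2.

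The cost is close to nothing: two short wording changes and possibly one bracket. Data collection, sample size and the hypothesis tests do not change. The 7-day limit needs only event timing, which the time-to-event analyses in SAP 4.3 already use. If the programming already follows Appendix A and Table 2, no reported result changes.

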#### **4.4 Methods to Manage Missing Data**

Reasonable efforts will be made to obtain complete data for all patients; however, missing observations may occur. The reasons for missing data will be reported (e.g., patient is deceased, lost to follow up, withdrew consent, missed follow-up visit, etc.).

The primary endpoint analysis of TLF will be performed using all available data. As a sensitivity analysis, a tipping point analysis will be performed to assess the impact of missing values from subjects with insufficient 12 month follow-up. This analysis will include the worst-case scenario as the most extreme case.

All secondary endpoint analyses will be performed using all available data.

### **5.0 ANALYSES AND SUMMARIES**

#### **5.1 Baseline and Other Summaries and Analyses**

##### **5.1.1 Study Conduct and Subject Disposition**

The frequency and percentage of subjects enrolled by site will be provided as a table.

A tabulation of patient disposition will be presented overall and by treatment arm, and will include the number of subjects screened, enrolled (randomized), and discontinued, with reasons for discontinuations (e.g., subject died, withdrew consent, was lost to follow-up, etc.) as documented on the case report form. Adherence to study inclusion/exclusion criteria and protocol deviations as documented on the case report form will be descriptively tabulated. A by-subject listing will include the reference data for these tables.

Compliance to 30-day, 6-month, and 1, 2, 3, 4, and 5-year follow-up visit schedules will be summarized for all subjects in the ITT analysis population and by site.

##### **5.1.2 Baseline Summaries**

Baseline patient characteristics will be presented descriptively and will be compared between two treatment arms using the methodology described in Section 4.3. Baseline measurements consist of subject demographics, general medical history, cardiovascular disease history, angina status, pre-procedural laboratory testing including cardiac biomarkers, and concomitant medications.

	FORM	Document No BIO-TMP-0702 Revision: 00
	TITLE Statistical Analysis Plan	Effective date: 16-Mar-2018 Department: BIO

### 5.1.3 Investigator Reported Index Procedure, Lesion, and Device Characteristics

Site reported index procedure characteristics, procedural medications, target lesion and device characteristics as reported in the case report forms will be presented descriptively for overall subjects and by treatment arm. Categorical and continuous variables will be compared between treatment arms using the methodology described in Section 4.3.

### 5.1.4 Core Lab Analyses

The Angiographic Core Lab Analysis will be summarized on a lesion level based on the ITT analysis set, and presented overall and by treatment arm. All angiographic analyses will consider target lesions only.

Continuous QCA variables will be compared between treatment arms using a one-way linear mixed model that accounts for the clustering effect of multiple lesions per subject. The model includes treatment as a fixed effect and subject as a random effect. Two-sided 95% confidence interval for the estimated mean difference between the two treatment arms and p-value from the linear mixed model will be reported for all continuous QCA data.

Binary core lab parameters will be compared between the treatment arms using a generalized linear mixed model that accounts for the clustering effect of multiple lesions per subject. The model includes treatment as a fixed effect and subject as a random effect. Two-sided 95% CI for the estimated difference and p-values will be reported.

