### 2.3 Angiographic Core Laboratory Variables

Pre-and post-procedure (final) coronary angiographic images will be analyzed by an independent Core Laboratory. Angiographic core lab variables include lesion morphology and/or QCA data as provided below:

- Pre-procedure morphology and QCA
- Final (post-procedure) morphology and QCA
- Final stent measurements
- Final stent edge measurements
- Final stent overlap/gap measurements

	FORM	Document No: BIO-TMP-0702 Revision: 00
	TITLE Statistical Analysis Plan	Effective date: 16-Mar-2018 Department: BIO

Pre-procedure and final QCA variables will be derived based on the following parameters from the Angiographic Core Laboratory (ACL) case report form:

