**Table 2: Derivation of QCA Data**

	Pre-Procedure Pre-procedure QCA section of the ACL Case Report Form	In-Segment Final QCA section of the ACL Case Report Form	In-Stent Final Stent Measurements section of the ACL Case Report Form
Minimum Lumen Diameter (MLD) [mm]	Pre-procedure MLD = Mean of pre-procedure QCA MLDs from Projections 1 and 2	In-segment MLD = Mean of Final QCA MLDs from Projections 1 and 2	In-stent MLD = Mean of Min Stent from Projection 1 and Min Stent from Projection 2
Reference Vessel Diameter (RVD) [mm]	Pre-procedure RVD (mm) = Mean of pre-procedure QCA interpolated RVDs (Inter Normal) from Projections 1 and 2	In-segment RVD (mm) = Mean of Final QCA Interpolated RVDs (Inter Normal) from Projections 1 and 2	In-stent RVD (mm) = Mean of Interpolated RVDs (Inter Stent) from Projections 1 and 2
Diameter Stenosis (DS) [mm]	$\%DS = 100 * (1 - \text{Pre-procedure MLD} / \text{Pre-procedure RVD})$	$\%DS = 100 * (1 - \text{In-segment MLD} / \text{In-segment RVD})$	$\%DS = 100 * (1 - \text{In-stent MLD} / \text{In-stent RVD})$
Acute Gain (mm)	N/A	Post-procedure In-segment MLD – Pre-procedure MLD	Post-procedure In-stent MLD – Pre-procedure MLD

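### The model for post-procedure QCA variables omits the pre-procedure vessel diameter and MLD that the core laboratory already derives, giving up some precision, mainly for post-procedure MLD

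*SAP*

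**What the plan says.** SAP 5.1.4 analyses core laboratory data at lesion level in the ITT set. For continuous measures: "Continuous QCA variables will be compared between treatment arms using a one-way linear mixed model that accounts for the clustering effect" of several lesions per subject. The terms are stated in full: "The model includes treatment as a fixed effect and subject as a random effect". The output is inferential as well as descriptive, since a 95% confidence interval and a "p-value from the linear mixed model will be reported for all continuous QCA data". Neither document adds a covariate to this model.

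The baselines are already in the data. SAP 2.3 lists "Pre-procedure morphology and QCA" among the core laboratory variables, and SAP Table 2 gives the derivations: "Pre-procedure MLD = Mean of pre-procedure QCA MLDs from Projections 1 and 2" and "Pre-procedure RVD (mm) = Mean of pre-procedure QCA interpolated RVDs (Inter Normal) from Projections 1 and 2". The same table defines in-stent acute gain as "Post-procedure In-stent MLD – Pre-procedure MLD", and calculates %DS by dividing the MLD by the RVD of the same segment.

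On timing, Protocol 7.3.1 calls for angiography before the intervention. Protocol 6.5 and 7.3.2 place randomisation after angiographic eligibility has been confirmed. Core laboratory technicians are blinded (Protocol 11.5.2).

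**The concern.** Vessel size should be a strong predictor of post-procedure MLD in this trial. Protocol 6.2.1.2 admits vessels from 2.25 to 4.00 mm, and Protocol 7.3.4 has the operator choose stent diameter by visual estimate, so the final lumen should largely follow the vessel. Randomisation is stratified by presentation, diabetes status and site (Protocol 11.5.1), not by vessel size. Neither the design nor the model therefore removes chance imbalance in vessel size from the MLD comparison.

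The pre-procedure values cannot be affected by the assigned stent, so they are legitimate covariates and need no new data collection. At stake is the width of the intervals for acute stent performance. There is also a smaller matter of coherence: the unadjusted comparisons of in-stent MLD and in-stent acute gain can give different between-arm differences on the same lesions, purely through chance imbalance in pre-procedure MLD.

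**Working it through.** **The plan's own figures.** The documents state no SD, effect size, power or precision target for any QCA variable. The only sample size to reproduce is the one for the primary endpoint (SAP 4.1.1: 6.5% in both arms, margin 3.575%, one-sided alpha 0.025, 2:1 allocation, 80% power).

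- Farrington-Manning restricted estimates under the null hypothesis: 0.0815 and 0.0458.
- s0 = √(0.0815 × 0.9185 + 2 × 0.0458 × 0.9542) ≈ 0.403; s1 = √(3 × 0.065 × 0.935) ≈ 0.427.
- Intervention n = ((1.960 × s0 + 0.842 × s1) / 0.03575)² ≈ 1032.4, so the total is 1.5 × 1032.4 ≈ 1548.6. Power at 1034:517 is 80.06%. This agrees with the stated 1551 and 80%.
- 1551 / 0.95 = 1632.6, against the stated 1632.

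The QCA point does not touch these figures.

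**Post-procedure MLD.** Inputs are 1088 and 544 subjects (SAP 4.1.1) and, as an assumption, one lesion per subject. The protocol allows up to three and gives no mean.

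- Unadjusted 95% half-width = 1.96 × √(1/1088 + 1/544) = 1.96 × 0.0525 = 0.103 SD.
- Adjusted half-width = 0.103 × √(1 − R²), with R assumed.

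| R (assumed) | Half-width (SD) | Narrowing | Equivalent extra lesions, 1/(1 − R²) − 1 |
|---|---|---|---|
| 0 | 0.103 | 0% | 0% |
| 0.2 | 0.101 | 2% | 4% |
| 0.3 | 0.098 | 5% | 10% |
| 0.5 | 0.089 | 13% | 33% |
| 0.7 | 0.074 | 29% | 96% |
| 0.8 | 0.062 | 40% | 178% |

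With an assumed SD of 0.3 to 0.6 mm, the half-width is 0.031 to 0.062 mm unadjusted, 0.029 to 0.059 mm at R = 0.3 and 0.022 to 0.044 mm at R = 0.7.

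**Chance imbalance in vessel size.** On the same assumptions, the 95% range of a chance difference in mean RVD is about ±0.10 SD. At an assumed correlation of 0.7, about 0.7 × 0.10 = 0.07 SD of that passes into the unadjusted MLD difference.

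**Acute gain.** Let k = SD(pre)/SD(post) and r = corr(pre, post), both assumed. In units of the post-procedure variance, the change score has variance 1 + k² − 2rk, and the analysis adjusted for pre-procedure MLD has residual variance 1 − r². The ratio of interval widths is √((1 − r²)/(1 + k² − 2rk)).

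- k = 0.75, r = 0.8: √(0.36/0.3625) = 0.997, a narrowing of 0.3%.
- k = 0.5, r = 0.4: √(0.84/0.85) = 0.994, a narrowing of 0.6%.
- k = 1.0, r = 0.4: √(0.84/1.20) = 0.837, a narrowing of 16%.
- k = 1.0, r = 0: √(1/2) = 0.707, a narrowing of 29%.

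Over k = 0.5, 0.75 and 1.0 and r from 0 to 0.8 in steps of 0.2, the contribution of MLD alone runs from 0.3% to 29%. Any contribution from RVD would be additional and cannot be derived from the documents.

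**Coherence.** Subtracting a covariate from the outcome changes only that covariate's slope. With pre-procedure MLD in both models and the same lesions, in-stent MLD and in-stent acute gain therefore give the same treatment coefficient.

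**The case against.** The strongest reply is that nothing in the trial turns on this. MLD, %DS and acute gain are not primary, powered secondary or other secondary endpoints. Only the binary lesion and device success, and procedure success built on lesion success, are, and SAP 5.3.2 gives those no formal hypothesis test. SAP 5.1.4 carries no alpha and no precision target. The unadjusted randomised comparison is unbiased, its interval already allows for chance imbalance, and its half-width is already about 0.10 SD. Pre- and post-procedure QCA appear in the same planned output (Table 35 in the SAP 7.1 list), so a reader could see an imbalance. All of this stands, and it limits the weight of the point.

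Three stronger readings are tempting, and the documents do not support them.

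- A reader might infer that all three outcomes ignore baseline. Acute gain does not, because pre-procedure MLD is part of its definition. What is missing is RVD and an estimated slope in place of a fixed slope of 1. Nor does the subtraction necessarily add noise: it lowers the variance relative to post-procedure MLD whenever r exceeds k/2.
- A reader might carry the larger narrowing figures for MLD across to %DS. SAP Table 2 already divides by a reference diameter, so much of the vessel-size variation should be removed.
- A reader might take a loss of 13% to 40% as established. That is the span for R from 0.5 to 0.8 only. Smaller values cannot be excluded, and at R = 0.2 the narrowing is 2%.

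Adjusting every post-procedure measure would also go too far. SAP 2.3 includes stent edge and overlap/gap measurements, for which there is no comparable argument.

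**Conclusion.** The point holds as an optional gain in efficiency. It does not identify an error, and no trial conclusion would change. The plan chooses to report intervals and p-values for these variables, and two baselines that should predict post-procedure MLD are left out of the model at no saving.

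For post-procedure MLD the interval would narrow by 2% to 40% for R between 0.2 and 0.8, with no narrowing if R is zero. For acute gain, pre-procedure MLD alone contributes 0.3% to 29% over the assumed grid. For %DS the gain is probably small and cannot be quantified. These sizes rest on assumed correlations and SD ratios, on full enrolment with readable films, and on one lesion per subject. With several lesions per subject, the gain would depend on how much of the variation between subjects and within subjects the baselines explain.

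**What to change.** In SAP 5.1.4, for post-procedure in-stent and in-segment MLD, acute gain and, optionally, %DS, add pre-procedure RVD and pre-procedure MLD as lesion-level fixed covariates, keeping the subject random effect. Leave pre-procedure variables and the stent edge and overlap/gap measurements unadjusted. Keep the unadjusted values in the descriptive table, and report by arm the number of lesions without pre-procedure QCA. Settle the change before unblinding so that the choice of covariates cannot appear data-driven.

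The cost is two terms in one model statement. The downside is that lesions without pre-procedure QCA drop out of the adjusted model, so it may rest on fewer lesions than the descriptive table. The documents do not say how many that would be, which is why the count should be reported.
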